## TITLE COLLAPSIBLE PESSARY FEASIBILITY TRIAL STATISTICAL ANALYSIS PLAN

## 1.0 OBJECTIVE

The Statistical Analysis Plan outlines the analysis groups, statistical tests, and success criteria for endpoints in the Collapsible Pessary Feasibility Trial.

## 2.0 SCOPE

Both primary and secondary endpoints are outlined.

- 2.1 Primary endpoints
  - 2.1.1 PFDI-20
  - 2.1.2 Adverse events
- 2.2 Secondary endpoints
  - 2.2.1 PFIQ-7
  - 2.2.2 PISQ-IR
  - 2.2.3 Objective assessment of ability to support the prolapse
  - 2.2.4 Global satisfaction
  - 2.2.5 Pain associated with insertion and removal
  - 2.2.6 Success and ease of fitting
  - 2.2.7 Frequency of self-management
  - 2.2.8 Ease of insertion and removal

## 3.0 REFERENCES

- 3.1 CP-002-01 Collapsible Pessary Feasibility Trial Protocol
- 3.2 CP-002-03 Collapsible Pessary Feasibility Trial Data Collection Form
- 3.3 SOP-1003 Design Control
- 3.4 F-3006 Test Report Template
- 3.5 SOP-1002 Quality Records
- 3.6 F-3010 Trial Adverse Event Log

## 4.0 DEFINITIONS

- 4.1 PFDI-20 – Pelvic Floor Distress Inventory-20
- 4.2 PFIQ-7 – Pelvic Floor Impact Questionnaire-7
- 4.3 PISQ-IR – Pelvic Organ Prolapse/Urinary Incontinence Sexual Questionnaire, IUGA-Revised
- 4.4 POP-Q – Pelvic Organ Prolapse Quantification
- 4.5 VAS – Visual Analogue Scale
- 4.6 CTCAE – Common Terminology Criteria for Adverse Events

\* Printed copies are uncontrolled unless otherwise identified \*

Before using this document, consult Grand Avenue to confirm current version before use.

CONFIDENTIAL

**TITLE COLLAPSIBLE PESSARY FEASIBILITY TRIAL STATISTICAL ANALYSIS PLAN****5.0 RESPONSIBILITIES**

- 5.1 Reia personnel and approved suppliers will be responsible for analyzing data.
- 5.2 Reia must maintain all quality records, including copies of data analysis performed by approved suppliers, according to SOP-1002 Quality Records.

**CONFIDENTIAL**

## TITLE COLLAPSIBLE PESSARY FEASIBILITY TRIAL STATISTICAL ANALYSIS PLAN

## 6.0 PFDI-20 (PRIMARY)

- 6.1 Endpoint
  - 6.1.1 Pelvic Floor Distress Inventory-20 (PFDI-20) of study pessary compared to current pessary
- 6.2 Data collection method
  - 6.2.1 The PFDI-20 is a validated instrument to assess the presence and bother of symptoms that pelvic floor disorders have on health-related quality of life in women. It is a 20-item questionnaire and the short form of the 46 question PFDI. There are three subscales: Urinary Distress Inventory 6 (UDI-6), Colorectal-Anal Distress Inventory 8 (CRADI-8), and the Pelvic Organ Prolapse Distress Inventory 6 (POFDI-6). The overall score range is 0-300. The higher the score, the greater the perceived impact that pelvic floor dysfunction has on a patient's life.
- 6.3 Analysis group
  - 6.3.1 In the primary analysis, all subjects who complete visit 1 will be included in this intention to treat group. Subjects who drop out of the study prior to visit 1 are not included in this analytic group. Subjects who drop out and are included in the analytic group will be assigned the lower (i.e., worse) limit score of 18.3 for the study pessary.
  - 6.3.2 A secondary per protocol analysis will not include subjects who drop out because of failure to be fit.
- 6.4 Data analysis plan
  - 6.4.1 For each subject, the difference in score for the PFDI-20 for the current and the study pessary will be calculated.
- 6.5 Success criteria
  - 6.5.1 Wiegersma et al. determined the minimal important change (MIC) in the PFDI-20 to demonstrate a clinical effect to be 13.5-18.3 points in women choosing conservative management of their prolapse. Each analysis is a one-sample, equivalence design. We use 2, one-sided t-tests, each with alpha set at .05 to test the composite null hypothesis that the mean difference score ( $\mu_{reia-control}$ ) between baseline (current pessary) and study pessary on the PFDI-20, is greater than 18.3, the upper equivalence limit, or lower than -18.3, the lower equivalence limit:

H01:  $\mu_{reia-control} > 18.3$  and H02:  $\mu_{reia-control} < -18.3$ . The alternative hypothesis is thus: HA:  $-18.3 \leq \mu_{reia-control} \leq 18.3$

We reject the null hypothesis when the maximum p value across both t-tests is less than .05.

\* Printed copies are uncontrolled unless otherwise identified \*

Before using this document, consult Grand Avenue to confirm current version before use.

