6.0 Procedures Involved

Methods

This is a non-randomized prospective trial. Treatment intervention will be non-blinded to the subject and the investigator. Subjects will serve as their own controls and enter the treatment phase of the study after a 1-month washout period of using their current pessary. Subjects will be recruited for this study from panels of patients in clinical practices specializing in Female Pelvic Medicine and Reconstructive Surgery (FPMRS). Inclusion will be based on pre-defined criteria outlined in "10.0 Inclusion and Exclusion Criteria."

The primary outcome measure will be the change in the scores of the Pelvic Floor Distress Inventory-20 (PFDI-20), administered first during the washout period while still using their current pessary and then at the conclusion of the treatment phase with the study pessary. The PFDI-20 is a validated health-related quality of life instrument to assess the *presence and bother of symptoms* in women with pelvic floor dysfunction. For women with relatively mild pelvic floor symptoms, a minimal important change (MIC) of between 13.5 and 18.3 points in the PFDI-20 score can be considered clinically relevant. At least fifty subjects will be enrolled, expecting that after drop-out and attrition at least 40 subjects will have completed the study. This provides power of .80 for a MIC equivalence limit of 17 points on the PFDI-20 scale.

There will not be discrimination based on race or ethnicity. It is anticipated that most participants will be post-menopausal as this reflects the demographic of women who suffer from this disorder.

The study will take place over 4 visits (Visit 0, Visit 1, Visit 2, and Visit 3).

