## TITLE COLLAPSIBLE PESSARY FEASIBILITY TRIAL STATISTICAL ANALYSIS PLAN

**9.0 ABILITY TO SUPPORT PROLAPSE (SECONDARY)**

- 9.1 Endpoint
  - 9.1.1 Objective assessment of the study pessary's ability to support anterior prolapse compared to current pessary
  - 9.1.2 Objective assessment of the study pessary's ability to support posterior prolapse compared to current pessary
- 9.2 Data collection method
  - 9.2.1 Modified POP-Q points Ba and Bp (measurements of anterior and posterior prolapse) will be measured during physical exam, with the pessary in situ.
- 9.3 Analysis group
  - 9.3.1 At most, for each subject two Ba and two Bp measurements will be collected for each of the current pessary and the study pessary.
  - 9.3.2 Subject's Ba and Bp measurements will be included in the comparative analysis if the subject has at least 1 data point for both the study pessary and their current pessary and did not drop out because of failure to fit.
- 9.4 Data analysis plan
  - 9.4.1 For each subject, average Ba and Bp scores for the current pessary and study pessary will be calculated.
  - 9.4.2 For each subject, a difference (current pessary – study pessary) in Ba and Bp scores will be calculated.
- 9.5 Reportable outcomes
  - 9.5.1 Average and standard deviation of the Ba and Bp with the current and study pessary will be reported.
  - 9.5.2 Mean difference (current pessary – study pessary) in Ba and Bp scores will be reported.
  - 9.5.3 We will use a two-tailed t-test to test the null hypothesis that the mean difference score between baseline (current pessary) and study pessary on the Ba is zero. This test is equivalent to a matched samples t-test. The p-value will be reported.
  - 9.5.4 We will use a two-tailed t-test to test the null hypothesis that the mean difference score between baseline (current pessary) and study pessary on the Bp is zero. This test is equivalent to a matched samples t-test. The p-value will be reported.
  - 9.5.5 Due to intra- and inter- observer variation in the measurements for Ba and Bp, a difference  $> 1.5$  cm is considered meaningful change. This analysis will be a one-sample, equivalence design. We will use 2, one-sided t-tests, to test the composite null hypothesis that the mean difference score between baseline (current pessary) and study pessary on the Ba measurement is less than or equal to  $-1.5$  cm and greater than or equal to  $1.5$  cm. The p-value will be reported.

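### The PFDI-20 dropout rule in SAP 6.3.1 contradicts 6.2.1 and 6.5.1; as printed, any dropout with a baseline above 18.3 is counted as improved

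*SAP*

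**What the plan says.** SAP 6.3.1 defines the primary intention-to-treat group as everyone who completes Visit 1. Those in that group who later drop out "will be assigned the lower (i.e., worse) limit score of 18.3 for the study pessary". Earlier losses are left out: "Subjects who drop out of the study prior to visit 1 are not included in this analytic group".

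Three neighbouring paragraphs bear on this rule:

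- **6.2.1** gives a 0-300 scale and its direction: "The higher the score, the greater the perceived impact that pelvic floor dysfunction has".
- **6.4.1** says that for each subject "the difference in score for the PFDI-20 for the current and the study pessary will be calculated", without saying which is subtracted from which.
- **6.5.1** takes 18.3 from the top of a published range for the minimal important change. It sets the null hypothesis that the mean difference, study pessary minus control, "is greater than 18.3, the upper equivalence limit, or lower than -18.3, the lower equivalence limit".

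From section 9 onward, where the SAP states a direction of subtraction, it is the opposite one. In 9.4.2, for example, "a difference (current pessary – study pessary) in Ba and Bp scores will be calculated".

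**The concern.** The dropout sentence disagrees with its own section in three ways. It calls 18.3 the lower limit, but 6.5.1 calls it the upper one. It equates lower with worse, but 6.2.1 says higher is worse. It calls 18.3 a score for the study pessary, but 18.3 is a change, and in 6.5.1 a limit on a mean difference.

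Three codings are therefore possible:

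- **A.** A difference (study minus current) of +18.3. This is the probable intent.
- **B.** A difference of -18.3. This is less likely, because it mixes the sign convention of the later sections with that of 6.5.1. Either convention used consistently gives A. B is possible only because 6.4.1 is silent on direction.
- **C.** A raw study-pessary score of 18.3. This is what the sentence literally says.

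The sentence fixes the data for the primary intention-to-treat test. Under C, a woman who stops because the device could not be retained or was uncomfortable is usually recorded as having improved. The study is single-arm and unblinded, so if the reading is settled after the data are seen, a choice that can change the verdict is made with the result in view.

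**Working it through.** **Sign under the literal reading (no assumptions needed).** Difference = 18.3 - baseline.

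| Baseline | 0 | 10 | 18.3 | 30 | 36.6 | 50 | 75 | 100 |
|---|---|---|---|---|---|---|---|---|
| Difference | +18.3 | +8.3 | 0 | -11.7 | -18.3 | -31.7 | -56.7 | -81.7 |

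**The plan's own power figure.** Protocol 6.0 states: "This provides power of .80 for a MIC equivalence limit of 17 points on the PFDI-20 scale". The sample is 40 completers, but no SD is given, so the figure can only be solved backwards. The exact power of two one-sided t-tests (n = 40, limit 17, alpha .05 each, true difference 0) equals 0.80 at an SD of 36.1. Two approximations:

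- Normal, both sides: 17 × √40 / (1.645 + 1.282) = 36.7.
- Normal, one side only: 17 × √40 / (1.645 + 0.842) = 43.2.

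I use 36.1. At the SAP limit of 18.3 it gives power of 0.87.

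**Number of dropouts.** Protocol 6.0: "At least fifty subjects will be enrolled, expecting that after drop-out and attrition at least 40 subjects will have completed the study". With exactly 50 enrolled, ten imputed subjects is the high end, because withdrawals during washout are not imputed. I also show five and two.

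**Fixed-data check.** There are 40 completers with mean m and SD s, and k dropouts all at a constant v.

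- N = 40 + k and M = (40m + kv)/N.
- S² = [39s² + 40(m - M)² + k(v - M)²]/(N - 1).
- t = (18.3 - |M|)/(S/√N) on N - 1 degrees of freedom, for the nearer limit.

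For m = +10, s = 36.1, k = 10:

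- A (v = +18.3): M = (400 + 183)/50 = 11.66, S = 32.4, t = 6.64/4.58 = 1.45, p = 0.077.
- B (v = -18.3): M = (400 - 183)/50 = 4.34, S = 34.2, t = 13.96/4.83 = 2.89, p = 0.003.
- C (assumed baselines of 60, so v = -41.7): M = (400 - 417)/50 = -0.34, S = 38.4, t = 17.96/5.43 = 3.31, p = 0.001.

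| Completer mean | Dropouts | A | B | C |
|---|---|---|---|---|
| +10 | 10 | 0.077 | 0.003 | 0.001 |
| +10 | 5 | 0.077 | 0.017 | 0.008 |
| +10 | 2 | 0.077 | 0.044 | 0.033 |
| 0 | 10 | 0.0015 | 0.0015 | 0.029 |
| -10 | 10 | 0.003 | 0.077 | 0.35 |

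At a completer mean of +10 with an SD of 25 or 30, all three pass.

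**Pass rates.** These are simulated at the 18.3 limit with SD 36.1, 40 completers and ten imputed. For C the dropout baselines are assumed gamma with mean 60 and coefficient of variation 0.3 to 1.0.

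| True completer mean | Dropouts omitted | A | B | C |
|---|---|---|---|---|
| -18.3 | 5% | 41% | 5% | about 0-1% |
| -10 | 41% | 89% | 41% | 8-11% |
| 0 | 87% | 93% | 93% | 49-60% |
| +10 | 41% | 41% | 89% | 77-94% |
| +18.3 | 5% | 5% | 41% | 51-68% |

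Over mean baselines of 30 to 90, the last C entry runs from 29% to 80%. With five or two imputed at +18.3, B passes 18% or 9% and C passes 22-28% or 10-11%. At -18.3, A passes 18% or 9%. As the SD rises from 25 to 40 with ten imputed, B at +18.3 falls from about 61% to 37%, and A at -18.3 does the same.

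**What A does and does not do.** A keeps the pass rate at 5% when completers are truly at +18.3. However, across SDs of 25 to 40, 2 to 15 dropouts and seven completer means from -18.3 to +18.3, it never turned a completers-only pass into a fail. With ten dropouts, the value assigned to each would have to reach about +47, +31 or +21 before the test fails, for completer means of 0, +5 and +8.

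**The case against.** The strongest reply is that the intent is obvious. The sentence itself labels the value as worse, and 18.3 appears elsewhere in section 6 only as a change or a limit on a change. 6.5.1 gives the direction as study minus control. No careful analyst would assign a near-best raw score as a penalty, and reading B needs a mix-up of sign conventions. On this view two words need correcting in a feasibility study.

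That the intent can be inferred stands, and B is the weakest of the three readings. But the inference runs against the printed words, and nothing elsewhere in the documents states the rule correctly.

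A second reply is that the numbers depend on the scenario. This also stands in part. With two dropouts, SD 36.1 and baselines of 60, A and C give different verdicts only for completer means of about +8.6 to +11.2 and about -10.3 to -7.3. At 0, +5 or +8 all three readings pass. With ten dropouts the ranges are much wider. The SD, the baseline mean and its spread are not in the documents; only the sign result is free of assumptions.

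A third reply is that easier passing on the improvement side may be clinically harmless. It may be, but the SAP tests both limits, so the effect belongs in the text.

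**Conclusion.** The concern holds as stated. SAP 6.3.1 is wrong as written, not merely short of detail: applied literally, it credits improvement to every dropout with a baseline above 18.3.

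The effect on the verdict depends on the SD, the number of dropouts, their baselines and the completer mean. Under the stated assumptions with ten imputed, the literal rule lifts the pass rate from 5% to 51-68% when completers are truly 18.3 points worse. It cuts it from 93% under the probable intent to 49-60% when they are unchanged. In some cases the verdict does not move, such as a completer mean of 0 in the fixed-data check.

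The probable intent, +18.3, has its own undisclosed asymmetry. With ten imputed and completers truly at -18.3, it raises the pass rate from 5% to 41%. Because the sentence governs the primary analysis, it must be corrected before the data are analysed.

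**What to change.** Required:

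- In 6.3.1, replace the rule with: dropouts are assigned a difference score (study minus current) of +18.3, the upper (worse) equivalence limit. The sponsor should confirm that this is what was meant.
- In 6.4.1, state that the difference is study pessary minus current pessary.
- Beside the rule, state that it protects only the upper (worse) margin and makes equivalence easier to declare when completers have improved.

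Optional: report the completers-only result next to the primary one, and add a tipping-point analysis that raises the assigned difference above +18.3. How dropouts who remain in the 6.3.2 per-protocol set are scored is a separate clarification.

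The cost is two sentences of rule, one of disclosure and, if wanted, one small table. No new data are needed. Compared with the literal reading, the correction can move the result either way: less favourable if completers have worsened, more favourable if they are unchanged or improved.

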vagina for epithelial erosions, and then reinsert the pessary.⁶ These steps are needed to avoid preventable complications associated with long term pessary use which have been reported as high as 56%⁷ and include vaginal erosion, bleeding, increased discharge, as well as discomfort and dysfunction in voiding and defecation.⁸ Furthermore, women who experience less severe forms of prolapse and who do not need the support of their pessary outside of strenuous physical activity often must wear their pessary when not necessary, which induces additional lifestyle impacts such as impairing a woman's ability to engage in sexual intercourse.

The two most commonly used pessaries on the market are the "ring with support" and the "Gellhorn" pessary. The Gellhorn pessary is clinically more effective to reduce the life impact of prolapse symptoms, 9 and once fit has longer continuation rates than the ring with support (10.5 years vs. 1.8 years). 10 Additionally, the Gellhorn successfully treated 71% of women at 3 months who failed treatment with the ring with support. 11 Yet most practitioners, particularly Ob/Gyn physicians who are not additionally specialized in FPMRS, preferentially prescribe the ring style pessaries because they are easier and more intuitive to use. The Reia Vaginal Pessary (study pessary) has been engineered to improve the comfort and ability of pessary removal and reinsertion by physicians and patients. The Reia Vaginal Pessary has a structural form similar to the Gellhorn, but is collapsible, and is hypothesized to be simpler and more comfortable to use than ring style pessaries. This hypothesis is preliminarily supported by data obtained in an early feasibility, in-office trial with 15 subjects (NCT04275089).

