8.5 Reportable outcomes

- 8.5.1 Average and standard deviation of the PFIQ-7 and PISQ-IR for the current and study pessary will be reported.
- 8.5.2 We will use a two-tailed t-test to test the null hypothesis that the mean difference score between baseline (current pessary) and study pessary on the PFIQ-7 is zero. This test is equivalent to a matched samples t-test. The p-value will be reported.
- 8.5.3 We will use a two-tailed t-test to test the null hypothesis that the mean difference between baseline (current pessary) and study pessary on the PISQ-IR is zero. This test is equivalent to a matched samples t-test. The p-value will be reported.

\* Printed copies are uncontrolled unless otherwise identified \*

Before using this document, consult Grand Avenue to confirm current version before use.

CONFIDENTIAL

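### SAP 6.3.1 puts PFDI-20 drop-outs on the wrong side as written; the two documents use different margins, and 6.5.1 plans no conclusion for a result beyond the improvement limit

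*SAP*

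**What the plan says.** SAP 6.2.1 sets the direction of the 0 to 300 scale: "The higher the score, the greater the perceived impact that pelvic floor dysfunction has on" the patient's life. SAP 6.5.1 defines the difference as study minus current pessary and tests it with two one-sided t-tests at .05. One null is a mean above +18.3; the other is a mean "or lower than -18.3, the lower equivalence limit". The only success rule is: "We reject the null hypothesis when the maximum p value across both t-tests is less than .05".

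SAP 6.3.1 keeps in the primary analysis everyone who completes Visit 1. Those who later drop out "will be assigned the lower (i.e., worse) limit score of 18.3 for the study pessary". SAP 6.3.2 adds a per-protocol analysis that removes only drop-outs who could not be fit.

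Protocol 6.0 (Methods) expects at least 50 enrolled and 40 completing, and states: "This provides power of .80 for a MIC equivalence limit of 17 points on the PFDI-20 scale". It gives no SD and no assumed true difference.

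For other scores the SAP also tests zero. For PFIQ-7 (8.5.2) the null is that the "mean difference score between baseline (current pessary) and study pessary on the PFIQ-7 is zero". For Ba (9.5.3) it is that the "mean difference score between baseline (current pessary) and study pessary on the Ba is zero", placed beside an equivalence test at 1.5 cm. Section 6 has no such test for PFDI-20.

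**The concern.** The drop-out rule contradicts the test it feeds. With study minus current and higher scores worse, the worse limit is the upper one, +18.3; the lower limit, -18.3, is improvement. The rule names the worse limit as the lower one, gives it a positive value, and calls it a score for the study pessary rather than a difference. Three programmers could code it three ways: a raw score of 18.3, a difference of -18.3, or a difference of +18.3. The first two credit most drop-outs with improvement, and the primary conclusion can turn on which is used.

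SAP 6.4.1 does not state the sign of the difference. Several later sections (for example 9.4.2 and 10.4.1) use current minus study, the reverse of 6.5.1. On that convention the worse limit would be the lower one, but its value would be -18.3.

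Two further points affect the same test. The protocol's power sentence uses a limit of 17 and the SAP uses 18.3. And 6.5.1 says nothing about a result that excludes worsening of 18.3 but crosses -18.3 on the improvement side.

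**Working it through.** **Inputs from the documents:** 40 completers, 50 enrolled, limit 17 and power .80 (protocol 6.0); limit 18.3 and one-sided .05 per test (SAP 6.5.1). **Assumed:** the SD of the paired difference, the drop-out count and the drop-out baseline scores.

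**1. The plan's own power figure.** It can only be solved backwards. With n = 40, limit 17, .05 per test and true difference 0, exact equivalence power is .80 at SD 36.1. The normal approximation gives 17 × √40 / (1.645 + 1.282) = 36.7. (The SD would be 32.3 with .025 per test, or 42.5 with a single one-sided test.) At SD 36.1 the SAP's limit of 18.3 gives power 0.87, so the protocol sentence does not describe the test in the SAP.

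**2. Three readings of 6.3.1.** Take 40 completers with a true mean of +18.3 (worse), SD 36.1, and 10 drop-outs. Expected analysed mean = (40 × 18.3 + 10 × d) / 50, where d is the mean drop-out difference.

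| Reading | d | Analysed mean | P(SAP success) |
|---|---|---|---|
| Difference of +18.3 | +18.3 | 18.3 | 0.05 |
| Difference of -18.3 | -18.3 | 549/50 = 11.0 | 0.41 |
| Raw score 18.3, baseline mean 60 (SD 36) | 18.3 - 60 = -41.7 | 315/50 = 6.3 | 0.64 to 0.68 |

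The last range depends on how negative simulated baselines are handled: set to 0 gives 0.64, truncated at 0 gives 0.68. Either brings the analysed mean slightly below 6.3. With baseline SD 30 and no such handling, the raw-score reading gives 0.24, 0.43, 0.65, 0.80 and 0.72 for baseline means of 20, 40, 60, 80 and 100.

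The raw-score reading can also hurt a sound device. With completers truly unchanged and a baseline mean of 80 (SD 30), success falls to 0.20, against 0.93 under the +18.3 difference.

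**3. What a constant of +18.3 does.** Let S and Q be the sum and the sum of squares of (difference - 18.3), and N the number analysed. The worsening-side statistic is t = S / √[(NQ - S²)/(N - 1)]. A drop-out at exactly +18.3 adds 0 to both S and Q. For 40 completers with sample mean 0 and SD 36.1, S = -732 and Q = 39 × 36.1² + 40 × 18.3² = 64,221. Then t = -3.21 with no drop-outs, -3.13 with 10 and -3.03 with 40, against critical values near -1.7. Simulated P(worsening side cleared) stays at about 0.93 with 0, 10, 20 or 40 drop-outs when completers are unchanged, and at about 0.74 when they are 5 worse. The full SAP rule rises from 0.87 with no drop-outs to 0.93 with 10, because the constant also shrinks the variance and moves the mean away from -18.3.

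**4. The improvement side.** With no drop-outs the 90% CI half-width is 1.685 × 36.1 / √40 = 9.6. An observed mean improvement above 18.3 - 9.6 = 8.7 therefore misses the criterion (11.6 at SD 25, 5.0 at SD 50).

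| True improvement | SAP rule | Worsening side alone |
|---|---|---|
| 0 | 0.87 | 0.93 |
| 5 | 0.73 | 0.99 |
| 10 | 0.41 | >0.99 |
| 18.3 | 0.05 | >0.99 |

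At a true analysed improvement of 18.3 or more the criterion is met at most 5% of the time, whatever the n or SD.

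**The case against.** On 6.3.1, the intent is plain: the text says *worse*, so a sensible analyst would use a +18.3 difference. That is probably what was meant. Nothing in the documents suggests that the sponsor plans to favour drop-outs. But the wording as it stands specifies something else, and the rule drives a primary conclusion. The per-protocol analysis does not cover the gap, because it removes only fit failures and so is not a completers-only result.

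On 6.5.1, a reader might infer that the success rule is itself an error, that a better device would be declared a failure, and that non-inferiority must replace equivalence. The documents do not support this. Both choose equivalence openly. Subjects are established pessary users, and the hypothesised gains are in comfort and ease of use; the SAP tests satisfaction, pain and ease against zero (10.5.3, 11.5.2, 11.5.3, 14.5.2, 14.5.3). The SAP says when the null is rejected; it does not say that a result beyond -18.3 is a device failure.

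No document predicts a large symptom gain. Protocol 3.0 does say "The Gellhorn pessary is clinically more effective to reduce the life impact of prolapse symptoms" and that the study pessary has a similar form, so some gain in ring users is possible. But it would be diluted. If only ring users improved, an overall mean of 8.7 among 40 completers would need 8.7 × 40 / 12 = 29 points each with 12 ring users, or 8.7 × 40 / 28 = 12.4 points with 28. Near no difference the present rule costs little (0.87 against 0.93).

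**Conclusion.** SAP 6.3.1 is wrong as written: it reverses the name of the limit and gives a near-best raw score in place of a difference. Under the assumptions in the working, a device whose completers are truly 18.3 points worse would meet the success rule about 64 to 68% of the time on the literal wording, and 41% on a -18.3 reading, instead of 5%. The contradiction needs no assumption; its size rests on the assumed SD, 10 drop-outs and their baseline scores.

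The intended +18.3 difference removes the error, but it leaves the worsening-side test almost blind to how many subjects drop out, so it is not enough alone.

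The 17 versus 18.3 margin is a separate conflict between the documents.

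The missing conclusion beyond -18.3 is a secondary reporting gap. It does not show that equivalence was the wrong design, and a move to non-inferiority as the success rule would be a trade-off for the sponsor to decide.

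**What to change.** Before outcome data are analysed:

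1. **SAP 6.3.1 and 6.4.1.** State that drop-outs after Visit 1 are assigned a difference, study minus current, of +18.3. Correct the word *lower* and state the sign of the difference. Add a sensitivity analysis that raises the drop-out differences above +18.3 until the conclusion changes. Report the number of drop-outs and a completers-only result beside the primary result.
2. **Margin and power.** Use one margin in both documents. Restate the protocol's power sentence with its assumed SD and true difference.
3. **SAP 6.5.1.** Keep equivalence as the success rule. Always report the mean difference with its 90% CI. Pre-specify that a result missing only the -18.3 limit is reported as not worse by more than the margin, equivalence not shown, together with whether the two-sided 95% CI lies wholly below 0.

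Make change 1 first. Under the literal wording the -18.3 limit gives some protection against spurious benefit from drop-outs, and a reading based on the worsening side alone would lose it.

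The cost is wording in two documents, a little more analysis and a less favourable reading of drop-outs. Sample size and data collection do not change.
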